On the treatment day, subjects will be hospitalized at the Research Intensive Care Unit for approximately 26 hours (taking preparation time prior to administration of the IMP into account). There will be continuous monitoring of symptoms, (intra-arterial) blood pressure, SpO₂ (%) and heart rate (ECG). Subjects will receive one venous catheter in the forearm. An arterial cannula will be placed in the radial artery, following local anesthesia using a lidocaine 1% solution for injection. Subjects will receive a single dose of study medication (AK1967 3, 6, or 12 mg/kg, or placebo), administered as an intravenous infusion over a 2-hour period. During the treatment day, serial blood samples of relevant pharmacokinetic and pharmacodynamic outcome parameters will be drawn from the arterial cannula. A 12-lead electrocardiogram will be performed 2 and 9 hours after start of IMP administration. Approximately 12 hours after initiation of drug administration, cannulas will be removed, and a pressure bandage will be applied to the site of arterial cannulation. Subjects stay overnight at the research Intensive Care Unit for continuous monitoring of vital signs. In the morning, a venous blood withdrawal is performed approximately 24 hours after start of IMP administration. Afterwards, the pressure bandage will be removed and subjects are released from the research unit. The subjects will return an additional 6 times for follow-up visits over the next 28 days (subjects will be checked for adverse events and blood samples will be obtained via venipuncture).

Ethical considerations relating to the clinical trial including the expected benefit to the individual subject or group of patients represented by the trial subjects as well as the nature and extent of burden and risks

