 Maximum decrease from baseline: (baseline - minimum value post-study drug administration) / baseline

≤ 0.5

Form Valid From: 08/03/2024

Form Version:

Record Title: Clinical Statistical Analysis Plan CT-P1-001

Record Title:

A frequency table by treatment dose will be generated for these categorized changes.

In addition, changes from "from within normal range to above normal range" will be evaluated and categorized as:

"changes to at least 1.5-time upper limit normal", "changes to at least twice upper limit normal".

A frequency table by treatment will be generated for these categorized changes from normal at baseline.

In case a value of one of these parameters is an outlier in a subject, this will be described separately.

12-lead ECG parameters

Non-quantifiable differences in ECG's deemed to be of clinical relevance by a clinical investigator will be registered as an (S)AE. For differences in ECG-related (S)AEs, the same ground-rules apply as those listed under reported number of adverse events and local tolerability (please refer to this section). Frequencies of overall interpretation (normal, abnormal and clinically not significant, abnormal and clinically significant) will be tabulated by treatment group and time point.

For numerically quantifiable differences in ECG-parameters (e.g. QTc-time, see the study protocol for a full overview), data distribution will be assessed using the Kolmogorov-Smirnov test and normal/non-normal distribution will be reported. Individual measurement timepoints will be expressed as both mean ± standard deviation (SD), as well as medians and interquartile ranges (IQR).

Extent of exposure

Total exposure [mg] and relative exposure [mg/kg] will be analyzed by descriptive summary statistics.

8.6 **Analysis of secondary endpoints**

Pharmacokinetic data analyses

The PK parameters will be analyzed by descriptive summary statistics. AK1967 concentration-time profiles for individual subjects will be analyzed with non-compartmental approaches using a validated commercially available software package (WinNonlin, version 8.4, Pharsight Corporation, Mountain View, CA). Nominal times will be used in the analysis. For data reported as BLQ and ALQ (below and above limit of quantification, respectively), the low and high limit of detection value will be used in the analysis.

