Pharmacokinetic (PK) parameters will be calculated including area under the concentration-time curve (AUC), maximum concentration (C_{max}), time to C_{max} (Tmax), and terminal half-life (t ½).

Form Valid From: 08/03/2024

Form Version:

Record Title: Clinical Statistical Analysis Plan CT-P1-001

The maximum drug concentration (C_{max}) and time to maximum drug concentration (T_{max}) will be determined from observed values. The area under the curve (AUC_{0-t}) will be calculated for PCZ plasma concentration-time profiles using the trapezoidal method derived from non-compartmental analysis from time zero (i.e. start of drug infusion) to the last detectable concentration.

Record Title:

Data distribution will be assessed using the Kolmogorov-Smirnov test and normal/non-normal distribution will be reported. Data will be displayed both tabular and graphically as means ± SD, as well as medians ± IQR. In case a value of one of these parameters is an outlier in a subject, this will be described separately.

Dose proportionality of C_{max} and $AUC_{0-\infty}$ of the different AK1967 dose groups will be calculated by dividing the specific PK parameter by the corresponding value in the lower dose groups and comparing with the corresponding fold change in dose. This is to assess which dosage groups should be reported as being non-dose proportional.

Pharmacokinetic parameters

The following parameters will be determined from the individual plasma concentration-time profiles of AK1967 using non-compartmental methods based on actual relative sampling times:

Single concentration data will be shown with the relevant number of decimal places as provided by the analytical lab. Derived parameters, as far as they do not present single concentrations such as C_{max} , will be listed with an appropriate number of relevant digits (at least 3).

Exposure parameters (C_{max} and AUC_{0-last}) will also be dose-normalized (i.e. divided by dose) for the determination of dose-dependency.

Descriptive pharmacokinetic analyses

The PK analysis will be performed for all active treatment groups.

The individual time courses of the plasma concentrations of AK1967 will be listed and summarized descriptively by treatment group and time point.

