Summary statistics by time point will be calculated including only those samples which were taken according to the pre-defined sampling schedule, i.e.: Day 1 (0.5, 1, 1.5, 2, 3, 4, 5, 6, 7, 8, 9, 10, 24 hour ± 2 mins), Day 2 (± 1 hour), Day 3 (± 3 hours), Day 7 (± 1 day), Day 14 (± 2 days), Day 21 ((± 3 days), and Day 28 (± 3 days).

For the calculation of summary statistics, when data is reported as BLQ and ALQ (below and above limit of quantification, respectively), the low and high limit of detection value will be used in the analysis to obtain the means, standard of deviations, coefficient of variation, medians and interquartile ranges.

Form Valid From: 08/03/2024

Form Version:

Record Title:

Record Title: Clinical Statistical Analysis Plan CT-P1-001

Individual plasma concentration-time profiles will be plotted for AK1967 (up to 6 profiles in one plot) for each dose group considering all subjects with available PK concentration data using actual relative sampling times. Mean (SD), as well as median (IQR) of AK1967 plasma concentrations will be plotted for all active treatment groups. Individual and geometric mean concentration versus time curves will be plotted using both linear and semi-logarithmic scaling.

Summary statistics will be calculated for each pharmacokinetic parameter by dose group based on PKs.

Pharmacodynamic data analyses (effects of AK1967 on DPP3 enzyme activity, concentration, reninangiotensin and adrenergic system metabolites)

- To determine the effects of AK1967 on DPP3 activity and concentration in healthy male volunteers.
- To determine the effects of AK1967 on renin-angiotensin system metabolites in healthy male volunteers.
- To determine the effects of AK1967 on circulating adrenergic metabolite concentrations in healthy male volunteers.
- To determine the effects of AK1967 on inflammatory cytokines, including, but not limited to TNF, IL-6, IL-8, IL-10.

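### If any AK1967 sample is reported above the assay's upper limit, SAP 8.6 substitutes that limit, which understates Cmax (and, much less, AUC) and biases the dose-proportionality ratios towards less than proportional

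*SAP*

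**What the plan says.** SAP 8.6, under Pharmacokinetic data analyses, gives one rule for both ends of the assay range: "For data reported as BLQ and ALQ (below and above limit of quantification, respectively), the low and high limit of detection value will be used". Under Descriptive pharmacokinetic analyses the rule is repeated for the summaries by time point: "the low and high limit of detection value will be used in the analysis to obtain the means, standard of deviations, coefficient of variation", and also for medians and interquartile ranges.

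Three other statements in SAP 8.6 depend on these values:

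- Cmax and Tmax are to be "determined from observed values".
- AUC is trapezoidal, "from time zero (i.e. start of drug infusion) to the last detectable concentration".
- Dose proportionality of Cmax and AUC is judged by dividing each group's value by that of the lower dose groups and "comparing with the corresponding fold change in dose". The stated purpose is: "This is to assess which dosage groups should be reported as being non-dose proportional". No interval or tolerance is given.

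Neither document states the upper limit of the AK1967 assay, an expected human Cmax, or whether above-range samples are diluted and re-assayed. SAP 6.3 lists a count of observations at or above the lower limit but none for the upper limit. No sensitivity analysis for ALQ values is planned.

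**The concern.** An ALQ result is a lower bound, and the true concentration can usually be recovered by diluting and re-assaying the sample. Entering the limit as if it had been measured does three things when it happens:

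- It understates the peak, and it gives every affected subject the same value, so variability shrinks as well.
- It conflicts with taking Cmax from observed values, because a substituted limit is not an observation.
- It acts on the highest concentrations, so it generally falls hardest on the top dose, which is the numerator of the 12:6 and 12:3 ratios.

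Because the SAP compares a bare point ratio with the dose fold, a shift caused only by the assay range could decide which dose group is reported as non-proportional. The same bias could hide a rise in exposure that is truly more than proportional. Pharmacokinetics is the first secondary objective.

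**Working it through.** The plan gives no figure to reproduce, so the check covers the direction of the effect and then its size under stated assumptions.

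**Inputs from the documents.** Doses of 3, 6 and 12 mg/kg, so the dose folds are 12/6 = 2, 6/3 = 2 and 12/3 = 4. Infusion over 2 h. Six active subjects per group. Sampling at 0.5 to 10 h, 24 h, and days 2, 3, 7, 14, 21 and 28 (SAP 3 and 8.6).

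**Assumptions, not in the documents.** Exactly dose-proportional one-compartment kinetics; volume 0.04 or 0.07 L/kg; half-life 24, 72 or 168 h; upper limit U set as a fraction f of the true 12 mg/kg Cmax.

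**Direction.** For C_high ≥ C_low, min(C_high, U)/min(C_low, U) ≤ C_high/C_low. The rule can lower a higher-to-lower ratio or leave it unchanged; it cannot raise it.

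**Cmax.** Under proportionality, Cmax is c at 6 mg/kg, 2c at 12 and c/2 at 3, with U = f × 2c. For f between 0.5 and 1 only the 12 mg/kg peak exceeds U, so the reported 12:6 ratio is 2f and the 12:3 ratio is 4f.

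**AUC.** With k = ln 2/half-life, C(t) = (D/2)/(kV) × (1 − e^(−kt)) during infusion and C(2) × e^(−k(t−2)) afterwards. Each sampled value is replaced by min(C, U), and the trapezoidal AUC to day 28 is recomputed. The ratios do not depend on V, because U scales with Cmax.

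| U / true 12 mg/kg Cmax | 12:6 Cmax (truth 2.0) | 12:3 Cmax (truth 4.0) | 12:6 AUC (truth 2.0) | ALQ samples per 12 mg/kg subject |
|---|---|---|---|---|
| 1.0 or more | 2.0 | 4.0 | 2.00 | 0 |
| 0.90 | 1.8 | 3.6 | 1.99 | 4–10 |
| 0.75 | 1.5 | 3.0 | 1.92–1.93 | 10–12 |
| 0.50 | 1.0 | 2.0 | 1.67–1.70 | 12–15 |

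**Clearance.** Clearance is dose/AUC, and at these limits the 6 mg/kg group is unaffected. Clearance at 12 mg/kg is therefore overstated by the factor 2.0 / (reported AUC ratio): 2.0/1.99 = 1.005, 2.0/1.93 = 1.04, and 2.0/1.70 to 2.0/1.67 = 1.18 to 1.20.

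**Lower limits.** With volume 0.05 L/kg and half-life 24 to 240 h, a limit at 40% of the 12 mg/kg Cmax caps the 6 mg/kg group too. The 6:3 Cmax ratio falls to 1.60 and the 12:6 ratio to 1.00.

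**Spread.** Take lognormal Cmax with log-SD 0.25 (true geometric CV 25%). A limit at the group median lowers the geometric mean by 9.5% and the geometric CV to 15%. A limit at 75% of the median lowers them by 26% and to 6%. The corresponding arithmetic CVs are about 13% and 5%. A limit above the median also has an effect: with a true CV of 30%, n = 6 and a limit at 1.25 times the 12 mg/kg median, about 22% of top-dose subjects are capped. The mean sample CV falls from 27.8% to 21.5% and the mean 12:6 Cmax ratio from 2.03 to 1.95.

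**The case against.** The rule covers only data reported as ALQ. It tells the analyst what to do with what the laboratory delivers, and it does not forbid dilution before reporting. If above-range samples are diluted routinely, or all samples are in range, the rule never operates. The documents do not say that any ALQ value is expected. This stands, and it makes the point conditional.

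A reader might infer that the SAP caps every high concentration, so that Cmax and AUC at 12 mg/kg are capped and proportionality is already biased. The documents do not support that. The upper limit and the expected Cmax are both absent, and every ratio above follows from an assumed limit. AUC is lowered rather than capped at a value: with the limit at 75% of Cmax, its ratio is still about 1.93 while the Cmax ratio is 1.5. Nor is the effect necessarily confined to the top dose.

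It is also fair to say that PK is a secondary, descriptive endpoint, that proportionality is not tested, and that the DSMB's listed issues (Protocol 12.10) do not include PK. Individual concentrations are listed and plotted, so a plateau at one repeated value could be noticed. These points limit the severity but do not rescue the rule. The SAP wrote an explicit instruction for ALQ results, and whenever it applies it enters a lower bound as a measured concentration, with no count of such values planned.

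**Conclusion.** The ALQ substitution is wrong as written, and its effect depends on ALQ results being reported. If they are, Cmax and its spread are understated, AUC is lowered much less, clearance is overstated, and higher-to-lower dose ratios can only move downwards, generally most where 12 mg/kg is the numerator. The direction follows from the arithmetic alone. The sizes in the table rest on exactly proportional one-compartment kinetics and on an assumed limit, so they illustrate the mechanism and do not estimate what will happen in this trial. With no ALQ result the effect is zero. A conditional bias in a descriptive secondary endpoint, cheap to remove, should be fixed before the PK analysis. It does not threaten the primary safety objective.

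**What to change.** In both sentences of SAP 8.6, remove the substitution for ALQ results and put in its place:

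> Samples above the upper limit of quantification are diluted within the validated range and re-assayed, and the diluted result is used. Any result still ALQ is flagged and counted by dose group and time point; the affected Cmax and AUC are reported as lower bounds (> value) and treated as right-censored in summaries and in the dose-proportionality assessment, and the subject is not dropped. A ratio that rests on a lower bound is not used to label a dose group non-dose proportional.

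The SAP should also state the upper limit itself. Its present wording flags values by limit of quantification but substitutes a limit of detection.

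Treating unresolved ALQ values as missing and excluding the subject is not a safe alternative, because it removes the highest exposures. Under the lognormal assumption above, with the limit at the median, exclusion lowers the geometric mean Cmax by about 18%, against 9.5% with substitution. At 75% of the median the figures are 34% and 26%. There only about 12.5% of subjects would be kept, and a group of six would be left empty with probability 0.875^6 = 0.45.

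**Cost.** Two sentences, slightly more analysis work, and repeat assays of samples around and after the end of infusion. In the scenarios above that is about 4 to 15 per top-dose subject, or 6 × 4 = 24 to 6 × 15 = 90 in all. Protocol 15.3.4 keeps samples for up to five years for analyses tied to the trial's objectives, so re-assay should be feasible where volume remains.

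### SAP 8.6 feeds below-limit samples into the non-compartmental analysis at a limit value, with no visible rule keeping them out of the terminal slope, and gives two contradictory time bases for that analysis

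*SAP*

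**What the plan says.** All of this is in SAP 8.6.

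- **Values outside the quantifiable range, in the NCA.** The paragraph that introduces the NCA of individual AK1967 profiles says that for such data "the low and high limit of detection value will be used in the analysis".
- **The same, in the summaries.** The descriptive PK subsection has its own copy for summary statistics: "the low and high limit of detection value will be used in the analysis to obtain the means" and the other summary measures. The rule in the NCA paragraph is therefore not merely a rule for tables.
- **Time basis.** The NCA paragraph says "Nominal times will be used in the analysis". The later subsection on PK parameters says they are obtained "using non-compartmental methods based on actual relative sampling times".
- **Truncation.** AUC0-t runs "from time zero (i.e. start of drug infusion) to the last detectable concentration". This limits that AUC only, and does not say whether a substituted value counts as detectable.
- **Dose proportionality.** Cmax and AUC0-inf are assessed by "dividing the specific PK parameter by the corresponding value in the lower dose groups and comparing with the corresponding fold change in dose".

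Elsewhere, SAP 5.2 names half-life and V as PK endpoints without saying whether V is Vz or Vss. SAP 7.1 limits the PK set to subjects whose data allow a reliable estimate of one or more parameters. That is an entry condition for the set, not a rule for choosing or accepting slope points.

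**The concern.** The terminal slope is a regression of log concentration on time over the last points of a profile. If late samples are below the limit and are replaced by a constant, the tail becomes artificially flat, and the slope then describes the assay limit as well as elimination. A lower dose reaches the limit sooner, so a half-life that is the same at every dose can be tabulated as differing between doses.

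Late samples below the limit are plausible. Sampling runs to day 28, and protocol 3.1 f describes the antibody's half-life in animals as short for an IgG1, though without a figure.

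Pharmacokinetics is the first secondary objective. No test of half-life or V between doses is planned, but both are summarised by dose group with six subjects per dose, where a false trend can be read. AUC0-inf also carries the slope, and it feeds the decision on which dose groups are reported as not dose proportional.

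The time-basis contradiction is separate and needs no assumption: two analysts following the same section could compute different parameters.

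**Working it through.** The documents give no LLOQ, LOD or human PK parameter, so there is no figure of the plan to reproduce. What follows is an illustration.

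**Inputs from the documents:** 3, 6 and 12 mg/kg; 2-hour infusion; the SAP sampling times (0.5 to 10 h, 24, 48 and 72 h, days 7, 14, 21 and 28); visit windows of up to ±3 days.

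**Assumed:** one compartment, V = 0.06 L/kg, LLOQ 0.01 to 1 µg/mL, no noise, linear trapezoid, and a slope chosen by best adjusted R² on at least 3 points after Cmax.

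**1. When does it matter?** Day 28 is below the limit only if half-life < 28 / log2[(dose/V)/LLOQ]. For 3 mg/kg, dose/V = 50 µg/mL; at LLOQ 0.1, 28/log2(500) = 28/8.97 = 3.12 d.

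| LLOQ (µg/mL) | 3 mg/kg | 6 mg/kg | 12 mg/kg |
|---|---|---|---|
| 0.01 | 2.28 d | 2.11 d | 1.96 d |
| 0.1 | 3.12 d | 2.81 d | 2.55 d |
| 1 | 4.96 d | 4.21 d | 3.66 d |

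Above these half-lives the substitution rule has no effect on the tail.

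**2. Late concentrations at a true half-life of 2 d.** After the infusion, C(t) = (dose/V) × [(e^(kT) − 1)/(kT)] × e^(−kt), with k = 0.3466 per day and T = 2/24 d, so the bracket is 1.0146. At 3 mg/kg, day 14 is 50 × 1.0146/128 = 0.396 µg/mL.

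| Dose | Day 7 | Day 14 | Day 21 | Day 28 |
|---|---|---|---|---|
| 3 mg/kg | 4.48 | 0.396 | 0.0350 | 0.0031 |
| 6 mg/kg | 8.97 | 0.793 | 0.0701 | 0.0062 |
| 12 mg/kg | 17.9 | 1.59 | 0.140 | 0.0124 |

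Samples below the limit at 3/6/12 mg/kg: 2/2/1 at LLOQ 0.1 and 3/3/2 at LLOQ 1.

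**3. NCA with the LLOQ inserted.** Half-life = ln 2/λz; Vz = dose/(λz × AUC0-inf); Vss = (dose/AUC0-inf) × (AUMC/AUC0-inf − T/2). Ratios are against the same NCA on quantifiable samples only.

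| 3/6/12 mg/kg, true half-life 2 d | LLOQ 0.1 | LLOQ 1 |
|---|---|---|
| Half-life (d) | 2.69/2.45/2.29 | 4.13/3.50/3.08 |
| R² of the slope | 0.96/0.97/0.98 | 0.88/0.89/0.92 |
| Vz ratio | 1.33/1.22/1.14 | 1.76/1.60/1.50 |
| Vss ratio | 1.06/1.03/1.01 | 1.66/1.32/1.17 |
| AUC0-inf, 12 v 3 mg/kg (true 4.0) | 3.97 | 3.62 |
| Half-life, below-limit samples left out | 2.00/2.00/2.00 | 2.00/2.00/2.00 |

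A two-compartment check (central V 0.05 L/kg, half the initial concentration falling with a 0.3 d half-life, terminal 2 d, 15% CV noise, 600 profiles per cell) gives median half-lives of 2.7/2.5/2.3 d and 4.3/3.6/3.1 d as written. With below-limit samples excluded they are 2.0/2.0/2.0 d and 1.9/1.9/2.0 d.

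**4. Direction.** Take a true half-life of 3 d, LLOQ 0.1, 3 mg/kg, with one third of the LLOQ inserted as an assumed LOD. Half-life is 2.78 d by best fit. On the last three points it is 14 × ln 2/ln(1.988/0.0333) = 2.37 d. The error is downward.

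**5. Time basis.** For a slope on equally spaced nominal days 7/14/21, the ratio of estimated to true half-life is 14/(14 + e21 − e7), where e is actual minus nominal day. With e7 uniform on ±1 and e21 on ±3, the median is 1.00 and the 95% range is 14/17.2 to 14/10.8, that is 0.81 to 1.30. In an extreme case with visits on days 16/21/25 entered as 14/21/28, a true 3 d becomes 3 × 14/9 = 4.67 d. This is mainly random error, and actual times remove it.

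**The case against.** **The absence of a slope rule is not proven.** This stands. SAP 8.6 announces a list ("The following parameters will be determined from the individual plasma concentration-time profiles of AK1967") that does not appear in the copy available to me, and SAP 7.2 refers to a data review plan that was not supplied. A reader might infer that the SAP has no slope rule at all; the documents support only that none is visible. Even if one exists, it would have to be reconciled with the substitution wording, and the time-basis conflict would remain.

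**The size is wholly assumed.** This also stands. With a longer half-life or a sensitive assay the effect is zero, and the direction and the worst-affected dose depend on the slope rule and on which limit is inserted.

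**Much larger errors should not be quoted.** Fitting the shortest non-flat segment gives half-lives of 7.1/4.7/3.5 d (LLOQ 0.1) and 10.8/7.4/21.1 d (LLOQ 1) for a true 2 d. These fits have adjusted R² of only 0.40 to 0.68, and an ordinary acceptance criterion would reject them. The best-fit errors are smaller but have R² of 0.88 to 0.98, so a fit cut-off alone would not catch them.

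**The volume error depends on the definition.** The Vz ratios cannot be read as the error in V generally. At LLOQ 0.1 the Vss error is at most 6%.

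**PK is descriptive, and the plan has safeguards.** The count of quantifiable observations (SAP 6.3), individual listings, semi-logarithmic plots and the separate description of outliers may expose a flat tail. They would not correct the tabulated parameters.

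**Conclusion.** The concern holds in a limited form. As written, SAP 8.6 puts limit values into the NCA and does not visibly keep them out of the terminal slope. If late samples are below the limit, half-life and Vz can be wrong by a dose-dependent amount, and AUC0-inf less so. Under the stated assumptions (true half-life 2 d, LLOQ inserted, best fit), half-life is overstated by about 15% to 35% at LLOQ 0.1 (2.29/2 to 2.69/2) and by about 54% to 107% at LLOQ 1 (3.08/2 to 4.13/2).

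A reader might infer that half-life will be overstated, always most at 3 mg/kg, or that the dose-proportionality result is invalid. The documents support neither. A lower LOD can reverse the direction, and in this example the 12 v 3 mg/kg AUC0-inf ratio moves only from 4.0 to 3.97 at LLOQ 0.1, reaching 3.62 at LLOQ 1.

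The contradiction between nominal and actual times is certain on the text. Its effect on half-life is mainly random. Both points should be fixed before the PK analysis; confidence is moderate because part of the relevant text was not available.

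**What to change.** Amend SAP 8.6 as follows:

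- (a) Use actual sampling times for all NCA parameters, and nominal times only for by-visit tables and mean plots.
- (b) Exclude values below the limit of quantification after the last quantifiable sample from the NCA, fit the terminal slope on quantifiable samples only, and end AUC0-t at the last quantifiable concentration.
- (c) Keep limit substitution only for the by-time summaries, and name the limit used. The text now flags samples against a limit of quantification but assigns them a limit of detection.
- (d) State how slope points are selected and accepted, and whether V is Vz or Vss. The particular criterion is a convention and the sponsor's choice; it adds to (b) and does not replace it. If the parameter list or the data review plan already holds a slope rule, cite it and reconcile it with the NCA paragraph.

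The cost is SAP wording and software settings, with no new samples or visits. The downside is that half-life, CL and V may be not estimable for a few profiles.
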